10.2.2 Research Assays

Serum samples collected for Immunogenicity assays prior to and post administration of GRT-R910 vaccine per the schedules of assessments ([Table 1](#), [Table 2](#), [Table 3](#)) will be assessed for SARS-CoV-2 antibody binding. Neutralizing antibody titers will be assessed against SARS-CoV-2 pseudoviruses. Peripheral blood mononuclear cells (PBMCs) will be extracted utilizing sodium heparin tubes, which are provided by Gritstone as noted in the laboratory manual and the corresponding requisition sheets. Multiple time points will be assessed via ex vivo IFN- γ ELISpot using overlapping 15mer peptide pools covering Spike and TCE regions to assess magnitude, breadth, and kinetics of T-cell responses. [REDACTED]

[REDACTED]

[REDACTED]

10.2.3 Samples for Genetic/Genomic Analysis

10.2.3.1 Genetic/Genomic Analysis

Remaining PBMC samples will be stored and may be used in secondary research for sequencing of DNA from B-cells to characterize B-cell receptors and monoclonal antibodies. The DNA data may be used to synthesize antigen-specific antibodies to characterize antibody binding. Secondary research samples may also be used for other genomic analysis including, but not limited to, single nucleotide polymorphism (SNP) arrays, transcriptomic analysis, evaluation of the immune response to the vaccine, and/or evaluation of any AE from the vaccine.

10.2.3.2 Genetic Privacy and Confidentiality

Any genetic data generated will be kept private. Informed consent permitting data sharing will be part of the consent process. Subjects will be informed that the evolution of genomic technology

and analytical methods raises the risk of re-identification, even when specimens are de-identified. No data that may identify specific subjects will be kept with the genetic data.

10.2.3.3 Management of Results

All genetic testing in this protocol will be performed for research only and is not performed in a Clinical Laboratory Improvement Amendments (CLIA) certified laboratory. Therefore, results will not be shared with the subjects.

10.2.3.4 Laboratory Specimen Preparation, Handling, and Storage

Instructions for specimen preparation, handling, and storage are included in protocol-specific MOP.

10.2.3.5 Laboratory Specimen Shipping

Instructions for specimen shipment are included in the protocol-specific MOP.

Specimen shipment will occur at intervals during the course of this study following all applicable International Air Transport Association (IATA) requirements and according to the specifics for storage temperature and documentation as detailed in the protocol-specific MOP.

11 ASSESSMENT OF SAFETY

11.1 Assessing and Recording Safety Parameters

Safety will be assessed by the frequency and severity of:

- SAEs occurring from the time of study consent throughout the entire study (reported to the sponsor or designee by the investigator within 24 hours of becoming aware of the SAE);
 - If the SAE occurs after signing of the ICF and before the first (prime) dose, it will be reported on the medical history eCRF. If the SAE occurs after the first (prime) dose, it will be reported on the AE eCRF.
- Solicited AEs (reactogenicity events occurring from the time GRT-R910 vaccination through 7 days after GRT-R910 vaccination);
- Reactogenicity local reactions (including erythema, induration/edema, pain, and tenderness);
- Reactogenicity systemic reactions (including fever, chills, fatigue, malaise, myalgia, arthralgia, headache, and nausea);
- Clinical safety laboratory AEs occurring from the time of GRT-R910 vaccination through approximately 7 days after GRT-R910 vaccination (parameters to be evaluated include WBC, Hb, PLT, ALT, AST, ALP, total bilirubin, CK, and creatinine);
- Unsolicited AEs (non-serious AEs occurring from the time of GRT-R910 vaccination through approximately 28 days after GRT-R910 vaccination);
- AESIs (including serologically or virologically confirmed SARS-CoV-2 infection and severity of COVID-19, PIMMCs, MAAEs, and NOCMCs occurring from the time of the first study vaccination throughout the entire study).

11.1.1 Adverse Events (AEs)

AE means any untoward medical occurrence associated with the use of an intervention in humans, whether or not considered intervention-related in a patient or clinical investigation subject administered a pharmaceutical product regardless of its causal relationship to the study treatment.

An AE can therefore be any unfavorable and unintended sign (including an abnormal laboratory finding), symptom or disease temporarily associated with the use of a medicinal (investigational) product. The occurrence of an AE may come to the attention of study personnel during study visits and interviews of a study recipient presenting for medical care, or upon review by a study monitor. AEs, including solicited local and systemic (subjective and quantitative) reactions, not meeting the protocol-defined criteria for SAEs will be recorded on the appropriate DCF and entered into the electronic case report form (eCRF). Information to be collected for unsolicited non-serious AEs includes event description, date of onset, licensed study physician's assessment of severity and relationship to GRT-R910 or alternate etiology (if not related to study product) (assessed only by those with the training and authority to make a diagnosis), date of resolution, seriousness, and outcome. AEs occurring during the trial collection and reporting period will be documented appropriately regardless of relationship to GRT-R910. AEs will be followed through resolution.

Any medical condition that is present at the time that the subject is screened will be considered as baseline and not reported as an AE. However, if the severity of any pre-existing medical condition increases, it should be recorded as an AE.

If an event meets both the criteria of a study endpoint and an adverse event, the event will be reported either as a study endpoint or as an AE (not both).

11.1.1.1 Solicited Adverse Events

Solicited AEs are anticipated local and systemic AEs for which consistent collection of information is desired. Study clinicians will follow and collect resolution information for any reactogenicity symptoms that are not resolved within 7 days post GRT-R910 vaccination.

Solicited AEs (i.e., reactogenicity) will be collected using a memory aid and recorded on the appropriate DCF from the time of GRT-R910 vaccination through 7 days after each GRT-R910 vaccination.

For this study, solicited AEs will be:

- Injection site pain
- Injection site tenderness
- Injection site erythema
- Injection site edema/induration
- Headache
- Fatigue
- Malaise
- Myalgia
- Arthralgia
- Nausea
- Fever
- Chills

11.1.1.2 Unsolicited Adverse Events

Unsolicited non-serious AEs will be captured for 28 days following each GRT-R910 vaccination. In addition, AESIs, including PIMMCs, MAAEs, and NOCMCs, will be captured throughout the entire study following GRT-R910 vaccination.

11.1.2 Definition of Serious Adverse Event (SAE)

An SAE is defined as follows: “An AE or suspected adverse reaction is considered serious if, in the view of either the participating site’s PI or appropriate sub-investigator or the sponsor, it results in any of the following outcomes:

- Death
- A life-threatening AE
- Inpatient hospitalization or prolongation of existing hospitalization
- A persistent or significant incapacity or substantial disruption of the ability to conduct normal life functions

- A congenital anomaly/birth defect

Important medical events that may not result in death, be life-threatening, or require hospitalization may be considered serious when, based upon appropriate medical judgment, they may jeopardize the patient or subject and may require medical or surgical intervention to prevent one of the outcomes listed in this definition. Examples of such medical events include allergic bronchospasm requiring intensive treatment in an emergency room or at home, blood dyscrasias or convulsions that do not result in inpatient hospitalization, or the development of drug dependency or drug abuse.

“Life-threatening” refers to an AE that at occurrence represents an immediate risk of death to a subject. An event that may cause death if it occurs in a more severe form is not considered life-threatening. Similarly, a hospital admission for an elective procedure is not considered an SAE.

All SAEs, as with any AE, will be assessed for severity and relationship to study intervention.

All SAEs will be recorded on the appropriate SAE DCF.

All SAEs will be followed through resolution or stabilization by a study clinician, licensed to make medical diagnoses

All SAEs will be reviewed and evaluated by Gritstone or designee by the investigator within 24 hours of becoming aware of the SAE and will be sent to the EC, if required. If the SAE occurs after signing of the ICF and before the first (prime) dose, it will be reported on the medical history eCRF. If the SAE occurs after the first (prime) dose, it will be reported on the AE eCRF.

11.1.3 Suspected Unexpected Serious Adverse Reaction (SUSAR)

A SUSAR is any SAE where a causal relationship with the study product is at least reasonably possible but is not listed in the Investigator’s Brochure (IB), Package Insert, and/or Summary of Product Characteristics.

11.1.4 Classification of an Adverse Event

The determination of seriousness, severity and causality will be made by an on-site investigator who is qualified (licensed) to diagnose AE information, provide a medical evaluation of AEs and classify AEs based upon medical judgment. This includes, but is not limited to, physicians, physician assistants and nurse practitioners.

11.1.4.1 Severity of Adverse Events

All AEs or SAEs will be assessed for severity, according to the toxicity grading scales in the US Food and Drug Administration guidance document entitled “Toxicity Grading Scale for Healthy Adult and Adolescent Volunteers Enrolled in Preventive Vaccine Clinical Trials.”

For AEs not included in the protocol-defined grading system, the following guidelines will be used to describe severity.

Mild (Grade 1): Events that are usually transient and may require only minimal or no treatment or therapeutic intervention and generally do not interfere with the subject’s usual activities of daily living.

Moderate (Grade 2): Events that are usually alleviated with additional therapeutic intervention. The event interferes with usual activities of daily living, causing discomfort but poses no significant or permanent risk of harm to the research subject.

Severe (Grade 3): Events interrupt usual activities of daily living, or significantly affects clinical status, or may require intensive therapeutic intervention. Severe events are usually incapacitating.

AEs characterized as intermittent require documentation of onset and duration of each episode. The start and stop date of each reported AE will be recorded on the appropriate DCF. Changes in the severity of an AE will be documented to allow an assessment of the duration of the event at each level of intensity.

All SAEs will be reviewed and evaluated by the protocol study team and Gritstone, and will be sent to the EC, if required.

11.1.4.2 Relationship to Study Product

For each reported adverse reaction, the participating site's PI or qualified designee must assess the relationship of the event to GRT-R910 using the following guidelines:

- Related – The AE is known to occur with the study intervention, there is a reasonable possibility that the study intervention caused the AE, or there is a temporal relationship between the study intervention and event. Reasonable possibility means that there is evidence to suggest a causal relationship between the study intervention and the AE.
- Not Related – There is not a reasonable possibility that the administration of the study product caused the event, there is no temporal relationship between the study product and event onset, or an alternate etiology has been established.

11.1.5 Adverse Events of Special Interest (AESIs)

An adverse event of special interest (serious or nonserious) is one of scientific and medical concern specific to the sponsor's product or program, for which ongoing monitoring and rapid communication by the investigator to the sponsor can be appropriate. Such an event might warrant further investigation in order to characterize and understand it. Depending on the nature of the event, rapid communication by the trial sponsor to other parties (e.g., regulators) might also be warranted. For this study, protocol-specified AESIs are serologically or virologically confirmed SARS-CoV-2 infection or severe COVID-19. AESIs also include the Brighton Collaboration AESIs relevant to vaccination that are listed below:

- NOCMCs – defined as any new ICD diagnosis (per current International Statistical Classification of Diseases and Related Health Problems) that is applied to the subject during the course of the study, after receipt of the study agent, that is expected to continue for at least 3 months and requires continued health care intervention.
- MAAEs – defined as hospitalization, an emergency room visit or an otherwise unscheduled visit to or from medical personnel for any reason.
- PIMMCs – These constitute a group of AEs that includes diseases which are clearly autoimmune in etiology and other inflammatory and/or neurologic disorders which may or may not have autoimmune etiology. PIMMCs that are of special interest for this study

are Brighton Collaboration AESIs relevant to vaccination that include: seizures, Guillain-Barre syndrome, acute disseminated encephalomyelitis, vasculitis, anaphylaxis, vaccine-associated enhanced respiratory disease, thrombocytopenia, and thrombotic events.

All AESIs are assessed, recorded, and followed as described above under AEs.

11.2 Reporting Procedures

Solicited local and systemic reactogenicity events will be documented and reported from the time of GRT-R910 vaccination through 7 days after GRT-R910 vaccination.

Clinical safety laboratory AEs will be documented and reported before GRT-R910 vaccination and 7 days after each GRT-R910 vaccination.

Unsolicited non-serious AEs will be documented and reported from the time of the GRT-R910 vaccination through 28 days after each GRT-R910 vaccination.

AESIs including PIMMCs/MAAEs/NOCMCs will be documented and reported from the time of the initial GRT-R910 vaccination throughout the entire study.

SAEs occurring after signing of the ICF will be recorded and reported to the sponsor or designee by the investigator within 24 hours of becoming aware of the SAE. If the SAE occurs after signing of the ICF and before the first (prime) dose, it will be reported on the medical history eCRF. If the SAE occurs after the first (prime) dose, it will be reported on the AE eCRF.

11.2.1 Reporting Serious Adverse Events and AESIs

SAEs will be followed until resolution even if this extends beyond the study-reporting period. Resolution of an AE is defined as the return to pretreatment status or stabilization of the condition with the expectation that it will remain chronic.

SAEs will be submitted immediately (within 24 hours of the site's awareness) to the sponsor via a CRO in paper form via facsimile or e-mail. Contacts for SAE reporting can be found in the Study Manual.

In addition to the SAE form, select SAE data fields must also be entered into the data coordinating center (DCC) system. Please see the protocol-specific MOP for details regarding this procedure.

Other supporting documentation of the event may be requested by the Gritstone/PPD Pharmacovigilance Group and should be provided as soon as possible.

Gritstone's Medical Monitor and Clinical Project Manager will be notified of the SAE by Gritstone/PPD Pharmacovigilance Group. Gritstone's Medical Monitor will review and assess the SAE for regulatory reporting and potential impact on study subject safety and protocol conduct.

At any time after completion of the study, if the site's PI or appropriate sub-investigator licensed to make medical diagnoses becomes aware of an SAE that is suspected to be related to study product, the site's PI or appropriate sub-investigator licensed to make medical diagnoses will report the event to the Gritstone/PPD Pharmacovigilance Group.

AESIs that meet SAE criteria will be reported on an SAE form within 24 hours of the site's awareness to the Gritstone/PPD Pharmacovigilance Group. In addition, for documentation and medical assessment purposes, AESIs that do not meet SAE criteria will also be reported on an SAE form within the period for AE reporting to the Gritstone/PPD Pharmacovigilance Group; however, the narrative will indicate that the AESI did not meet SAE criteria.

11.2.2 Regulatory Reporting for Studies Conducted Under Gritstone-Sponsored CTA

Following notification from the participating site's PI or appropriate sub-investigator, Gritstone, as the CTA sponsor, will report any SUSAR in a safety report and will notify all participating PIs (i.e., all PIs to whom the sponsor is providing study product under its Investigational New Drug Application [IND]) of potential serious risks from clinical studies or any other source, as soon as possible. Gritstone will report to the MHRA any unexpected fatal or life-threatening suspected adverse reaction as soon as possible, but in no case later than 7 calendar days after the sponsor's initial receipt of the information. If the event is not fatal or life-threatening, the safety report will be submitted within 15 calendar days after the sponsor determines that the information qualifies for reporting as specified in International Council for Harmonisation (ICH)/GCP guidelines. Relevant follow up information to a safety report will be submitted as soon as the information is available. Upon request from MHRA, Gritstone will submit to MHRA any additional data or information that the agency deems necessary, as soon as possible, but in no case later than 15 calendar days after receiving the request.

All SAEs designated as "not related" to study product(s), will be reported to the MHRA at least annually in a summary format.

11.3 Type and Duration of Follow-up of Subjects After Adverse Events

AEs will be collected, assessed, and followed from initial recognition of the AE through 28 days after each GRT-R910 vaccination.

SAEs will be collected, assessed, and followed through resolution even if duration of follow-up goes beyond the protocol-defined follow-up period.

Resolution of AEs/SAEs/AESIs including PIMMCs/MAAEs/NOCMCs is defined as the return to pre-treatment status or stabilization of the condition with the expectation that it will remain chronic.

Follow-up procedures, evaluations, and outcomes will be recorded on appropriate DCF and entered into the eCRF.

11.3.1 Procedures to be Followed in the Event of Abnormal Laboratory Test Values or Abnormal Clinical Findings

The site's PI or appropriate sub-investigator is responsible for recording all AE/SAEs that are observed or reported during this trial, regardless of relationship to study product. AE/SAEs, abnormal laboratory test values or abnormal clinical findings will be collected, assessed, documented, reported, and followed appropriately, using a local laboratory as necessary. In determining eligibility, refer to [Sections 7.1](#) and [7.2](#) and the protocol-specific MOP.

11.4 Sentinel Dosing

Sentinel dosing in Cohorts 1 and 2 will consist of 2 volunteers in each cohort dosed 72 hours ahead of the remainder of each cohort, with the remainder of the volunteers dosed at the same dose level only if no halting rules are met. Enrollment in Cohort 2 will only proceed if safety data from all volunteers in Cohort 1 meet the dose-escalation rules. There will be no sentinel dosing in Cohorts 3, 4, and 6.

11.5 Dose Escalation

After the planned 10 volunteers enrolled in Cohort 1 have completed their 7-day reactogenicity assessments, Day 8 safety laboratory assessments after vaccination, and no study halting rules have been met, GRT-R910 will be escalated to 30 mcg in Cohort 2.

Determinations of when to move from sentinels to the rest of the cohort, and for dose escalation in Cohort 2, are made by the protocol team consisting of all investigators and selected Gritstone team members (sub-investigators may be included).

11.6 Halting Rules

In the event a halting rule is met, all dosing will immediately stop, and a substantial amendment must be submitted and approved by the competent authority where required prior to allowing restart of any dosing:

- An unscheduled safety analysis will be required for approval of further enrollment, and
- Further administration of the vaccines is suspended for ALL subjects until an assessment by the study team takes place.
- All dosing will immediately stop.

11.6.1 Study Halting Criteria

- Any subject experiences an SAE within 28 days after administration of GRT-R910, considered related to GRT-R910.
- Any subject experiences laryngospasm, bronchospasm, or anaphylaxis within 24 hours after administration of GRT-R910 that is considered related to GRT-R910.
- Any subject experiences ulceration, abscess, or necrosis at the injection site related to GRT-R910 administration.
- Four (4) or more subjects experience an allergic reaction such as generalized urticaria (defined as occurring at 3 or more body parts) within 72 hours (3 days) after administration of GRT-R910 that is considered related to GRT-R910.
- Five (5) or more subjects after prime dosing experience:
 - A Grade 3 unsolicited AE in the same preferred terms based on the Medical Dictionary for Regulatory Activities (MedDRA) coding that lasts at least 48 hours after administration of GRT-R910 and is considered related to GRT-R910.
 - A clinical laboratory abnormality within 28 days after administration of GRT-R910 that is classified as a Grade 3 AE and is considered related to GRT-R910.

- Five (5) or more subjects after booster dosing experience:
 - A Grade 3 unsolicited AE in the same preferred terms based on the MedDRA coding that lasts at least 48 hours after administration of GRT-R910 and is considered related to GRT-R910.
 - A clinical laboratory abnormality within 28 days after administration of GRT-R910 that is classified as a Grade 3 AE and is considered related to GRT-R910.

GRT-R910 administration and enrollment may resume only after review of the AEs that caused the halt in dosing results in recommendation to permit further study GRT-R910 administration and enrollments, and a substantial amendment has been submitted and approved prior to allowing restart of any dosing.

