4.3 Benefit/Risk Assessment

The benefit/risk assessment for a SAM-directed vaccine (including GRT-R910) to target SARS-CoV-2 is currently being evaluated in a first-in-human Phase 1 study assessing heterologous prime-boost (ChAd prime followed by SAM boost) and homologous prime-boost (SAM prime followed by SAM boost) in naïve subjects above the age of 18 years (NCT04776317). Based on additional prior clinical experience with SAM vectors used as boosts (up to 8 boosts per patient) currently in Phase 2 in patients with advanced cancers (NCT03953235, NCT03639714), the vaccinations are expected to result in mild to moderate local reactions as well as systemic reactions such as mild flu-like symptoms. Based on preclinical data in non-human primates, on clinical data in patients with cancer and on data from other SARS-CoV-2 vaccines, the reactogenicity to SAM-based vectors in general, and GRT-R910, is expected to be lower in older adult subjects compared to younger ones. We further anticipate that T-cell responses will be less robust in older adult subjects due to T-cell senescence. The overall goal of this approach is to ensure safety in the older adult population without compromising the ability of the trial to rapidly identify the optimal dose to ensure a robust T-cell activation in older subjects.

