The reactogenicity and immunogenicity data assessed after the first dose of GRT-R910 will inform selection of the GRT-R910 dose to be tested in future studies. The 10 mcg dose of GRT-R910 was selected for use in Cohorts 3, 4, and 6 by evaluating the balance of immunogenicity and reactogenicity of a single dose of GRT-R910 in Cohorts 1 and 2.

Injection will be given intramuscularly as a prime-boost at least 2 months after the last administration of a SARS-CoV-2 vaccine either approved for emergency supply or approved for use by the MHRA for prevention of SARS-CoV-2. Subjects should refrain from a subsequent boost with an emergency supply or approved SARS-CoV-2 vaccine for a minimum of 4 months after the second dose of study vaccine.

Figure 1 Study Flow Chart

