Pre-administration reactogenicity assessments will be performed prior to each study vaccination to establish baseline, then the study vaccination will be given.

Subjects will be observed in the clinic for at least 45 minutes after GRT-R910 vaccination. The vaccination site will be examined, post-administration reactogenicity assessments will be performed, and any AE/SAEs will be assessed and recorded on the appropriate data collection form prior to discharge from the clinic. AESIs, including serologically or virologically confirmed SARS-CoV-2 infection and severity of COVID-19, PIMMCs, MAAEs, and NOCMCs will be collected from the time of first vaccination throughout the entire study. Any SAE occurring after signing of the ICF will be recorded and reported to the sponsor or designee by the investigator

within 24 hours of becoming aware of the SAE. If the SAE occurs after signing of the ICF and before the first (prime) dose, it will be reported on the medical history electronic case report form (eCRF). If the SAE occurs after the first (prime) dose, it will be reported on the AE eCRF.

All subjects will complete a subject memory aid through 7 days after each GRT-R910 vaccination. Subject memory aids will be reviewed with the subjects for AEs (solicited local and systemic reactions and unsolicited AEs) during telephone, e-mail, or text contacts or at a clinic visit, as appropriate.

Reactogenicity assessments will include an assessment of solicited AEs occurring from the time of GRT-R910 vaccination on Day 1 through Day 8 after GRT-R910 vaccination, which includes an assessment of local reactions including erythema (redness), induration (hardness)/edema (swelling), pain, and tenderness as well as systemic reactions including fever, chills (feverishness), fatigue (tiredness), malaise (general unwell feeling), myalgia (body aches/muscular pain exclusive of the injection site), arthralgia (joint pain exclusive of the injection site), headache, and nausea.

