12.3 Treatment Assignment Procedures

12.3.1 Assignment Procedures

Cohorts 1 and 2 will be enrolled sequentially following dose-escalation rules. Two sentinels in each cohort will be observed for 72 hours for safety in each dose cohort. If no halting rules are met after the 2 sentinels in each cohort have been observed for 72 hours after study vaccination, the remaining 8 volunteers will be enrolled in each cohort.

The dose for Cohorts 3, 4, and 6 was selected from Cohorts 1 and 2 after evaluation of reactogenicity, safety, and initial immunogenicity. Dose selection will be determined by the Gritstone clinical team in consultation with the PI(s). Cohorts 3, 4, and 6 will be enrolled in parallel. There will be no sentinel dosing in Cohorts 3, 4, and 6.

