9.1.3. Study Halting Rules

Section 11.6 of the protocol provides criteria that would trigger an immediate halt to dosing for all subjects until an assessment by the study team has taken place, and an amendment is submitted to, and approved by, the competent authority. Both solicited and unsolicited adverse events, and which (if any) study halting criteria they meet, are collected on the Study Halting Rule CRF, and will be presented in a data listing.

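### The count-based Grade 3 halting criteria leave out solicited reactions, so a cluster of them not judged serious or allergic requires no cohort-level dosing decision; this is of most concern in Cohort 6

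*Protocol*

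**What the plan says.** Protocol 11.6.1 has two count-based Grade 3 criteria, each stated once for prime and once for booster dosing and each needing five or more subjects. One is "A Grade 3 unsolicited AE in the same preferred terms based on the Medical Dictionary for Regulatory Activities (MedDRA) coding", related and lasting at least 48 hours. The other is a related Grade 3 laboratory abnormality within 28 days. The remaining criteria are a related SAE, airway or anaphylactic events, injection-site ulceration, abscess or necrosis, and four or more allergic reactions.

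Protocol 11.1.1.1 makes solicited AEs a separate class of 12 local and systemic terms. SAP 9.1.2 moves a reaction out of that class only if it fits no listed category or is serious. SAP 9.1.3 says that "Both solicited and unsolicited adverse events, and which (if any) study halting criteria they meet, are collected on the Study Halting Rule CRF", but the criteria it refers to are those of protocol 11.6.

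Protocol 11.5 says that determinations on moving from sentinels to the rest of a cohort and "for dose escalation in Cohort 2, are made by the protocol team consisting of all investigators" and selected sponsor staff. For the later cohorts, protocol 12.3.1 states: "Cohorts 3, 4, and 6 will be enrolled in parallel. There will be no sentinel dosing in Cohorts 3, 4, and 6". Their 10 mcg dose was chosen "by evaluating the balance of immunogenicity and reactogenicity of a single dose of GRT-R910 in Cohorts 1 and 2" (6.1), and both of those cohorts are aged 60 or over. Section 4.3 says that "the reactogenicity to SAM-based vectors in general, and GRT-R910, is expected to be lower in older adult subjects compared to younger ones".

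**The concern.** Solicited local and systemic reactions are the first two primary outcome measures, and sections 4.3 and 4.3.3 expect them to be the main toxicity. A run of severe ones after the prime is what should make a team stop and think before giving the booster. Nothing in 11.6.1 counts them, so whether anyone looks across the cohort before the remaining doses are given is left to discretion.

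The gap is study-wide, because release from sentinels in Cohorts 1 and 2 uses the same halting rules. There, however, 11.5 requires a team determination, and escalation waits for 7-day reactogenicity data. Cohorts 3, 4 and 6 have no such step. Cohort 6 stands out because it is the only cohort aged 18–59, its dose comes from older adults after a single dose, and all 10 subjects are due a second dose at 28 days. The plan itself expects younger adults to react more.

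**Working it through.** **Step 1: can a solicited reaction meet a criterion?** Take a related, non-serious Grade 3 fever, fatigue, myalgia, headache or injection-site pain.

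- Grade 3 count: unsolicited AEs only, so no.
- Laboratory count: no.
- Related SAE: only if judged serious.
- Airway, anaphylaxis or allergy criteria: no.
- Ulceration, abscess or necrosis: none is a listed solicited term.

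The number of such reactions that triggers a required decision is therefore none, from 0 of 10 up to 10 of 10.

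**Step 2: the plan's own figure.** Protocol 12.2 gives 89% for at least 1 event in 10 subjects at a 20% rate. Check: 1 − 0.8^10 = 1 − 0.1074 = 0.8926. This and all 21 cells of Table 5 reproduce.

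**Step 3: what a count rule would do in one cohort.** X is binomial with n = 10. The documents give no Grade 3 rates, so the rates p are assumed and shown as a range, per term and per dose.

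| p | P(X ≥ 1) | P(X ≥ 3) | P(X ≥ 5) |
|---|---|---|---|
| 5% | 40.1% | 1.2% | 0.01% |
| 10% | 65.1% | 7.0% | 0.2% |
| 20% | 89.3% | 32.2% | 3.3% |
| 30% | 97.2% | 61.7% | 15.0% |
| 50% | 99.9% | 94.5% | 62.3% |

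The existing count of five has no per-cohort denominator. Across all 30 subjects of Cohorts 3, 4 and 6 it would act with probability 74.5% at 20%, but only if all three cohorts had that rate. If the excess is confined to Cohort 6, the relevant column is the last one.

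**Step 4: a 48-hour condition.** Section 4.3.3 describes these reactions as transient. At a 30% rate, suppose 10%, 25% or 50% of reactions last 48 hours, so that p = 0.03, 0.075 or 0.15. Then P(X ≥ 3) = 0.3%, 3.4% or 18.0%, against 61.7% without the condition. A duration condition would remove most of the rule's effect.

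**Step 5: how often Cohort 6 would pause over both doses.** Let q = P(X ≥ 3) per term and dose. With 12 independent terms and 2 doses, the chance is 1 − (1 − q)^24. If all terms occur together within a dose, it is 1 − (1 − q)^2.

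| Per-term rate | q | Independent | Fully dependent |
|---|---|---|---|
| 1% | 0.000114 | 0.3% | 0.02% |
| 2% | 0.000864 | 2.1% | 0.2% |
| 5% | 0.0115 | 24.2% | 2.3% |
| 10% | 0.0702 | about 83% | about 14% |

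The independent column is an upper marker. At 5% it implies that 1 − 0.95^12 = 46% of subjects have some Grade 3 reaction per dose, and at 10% that 1 − 0.9^12 = 72% do. A review may well be warranted at that level.

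**Step 6: timing in one subject.** Day 8 review to Day 29 booster is 29 − 8 = 21 days. The shortest in-window gap is (29 − 3) − (8 + 2) = 16 days. The last in-window booster day is 29 + 3 = Day 32.

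**The case against.** The strongest case against is that this is a coherent design choice. Solicited reactions are anticipated and expected to be mild to moderate and transient. A halt under 11.6 stops all dosing and needs a substantial amendment to restart, so reserving it for serious or unexpected events makes sense. That stands, and it is why the remedy should be a pause and not a new halting criterion.

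A reader might infer that severe solicited reactions go unreviewed. The documents do not support that. Section 10.1 says that "Subject memory aids will be reviewed with the subjects for AEs (solicited local and systemic reactions and unsolicited AEs"), and site investigators grade and review AEs (16.2). Medically attended reactions are AESIs (11.1.5), and "AESIs that do not meet SAE criteria will also be reported on an SAE form within the period for AE reporting". Individual removal (7.2.3), early termination (7.2.5) and ad hoc analyses (protocol 18.1, SAP 10) are also available. All of these are case-level or discretionary; none requires a decision on solicited grades across a cohort.

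A reader might also infer that no Grade 3 solicited reaction can stop dosing. That goes too far. The SAE definition in 11.1.2 includes substantial disruption of normal life functions, and 11.1.4.1 describes Grade 3 events as usually incapacitating. An investigator or the sponsor may judge one serious, and a single related SAE within 28 days halts the study. Not every Grade 3 reaction qualifies, so the gap is narrower but remains.

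Nor do the documents show that 10 mcg is wrong for younger adults. It is the lower dose tested, and section 4.3.3 supports up to 100 mcg in healthy subjects. It also reports that 13 subjects had received GRT-R910 in the first-in-human study, which section 4.3 says enrols adults over 18, with safety consistent with the platform. Their ages and doses are not stated, so this tempers the concern without settling it.

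Finally, the change may have little left to act on. The SAP revision history has Cohort 6 present by May 2022, and SAP version 5.0 dates from June 2023. Dosing may be late or complete; the documents do not say.

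**Conclusion.** The concern holds in a limited form. A cluster of related Grade 3 solicited reactions that investigators do not judge serious or allergic requires no cohort-level dosing decision under 11.6.1, however large the cluster. Cohorts 3, 4 and 6 share the gap. That it is of most concern in Cohort 6 is a reasoned judgement from age, the source of the dose data and section 4.3, not something the documents measure.

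The change is worth making if doses remain, with medium confidence. The figures rest on assumed Grade 3 rates, on binomial counts in 10 subjects and, for the pause rates, on a stated range of dependence between terms with the two doses treated as independent. The 3-of-10 threshold is a clinical judgement that the sponsor may adjust.

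**What to change.** For doses still to be given in Cohort 6, and optionally in Cohorts 3 and 4, add to 11.6 a pause separate from the 11.6.1 criteria:

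- **Trigger:** for example, 3 or more of the 10 subjects in a cohort with the same related solicited reaction at Grade 3 or higher after the same dose number. Set no minimum duration.
- **Action:** remaining doses in that cohort wait for a documented review of the solicited grades by the 11.5 protocol team. Extend 11.5 to cover this review.
- **Restart:** on the team's decision, with no substantial amendment unless an 11.6.1 criterion is met or the dose is changed.
- **Late boosters:** state that a booster delayed by this pause may be given after Day 32 within a set limit and still count for the immunogenicity population.

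The cost is one protocol amendment and one added option on the Study Halting Rule CRF, which already collects solicited events. No visits or data are added. The downside is an occasional team review, at the frequencies in step 5 of the working, and possible late boosters. The 16 to 21 days in one subject often leave room. With staggered enrolment, or a trigger after boosters, another subject may be due at once. Without the late-booster rule, such subjects could fall out of the immunogenicity population as protocol 12.4 defines it. SAP 4.5.4 uses a wider placeholder definition, so the two should be aligned.
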